- 7) This patient will be readmitted to the hospital in the next 3 months
- 8) This patient will die during the next 3 months

Safety

The greatest risk in administering a diuretic is the potential to make the patient volume depleted via diuresis. In order to ensure that this does not happen, the urine output after the furosemide bolus will be matched ml for ml with isotonic saline. The treating team has the option of replacing less isotonic saline if the treating team wants volume to be removed. However, the default procedure will conduct this matched replacement for six hours after the furosemide bolus. Since furosemide induces the production of hypotonic urine, a milliliter for milliliter matched repletion of normal saline guarantees that the patient cannot become volume depleted.

Furosemide is routinely given to patients with AKI, particularly those with acute tubular necrosis. Furosemide has not been shown to be harmful nor helpful in patients suffering from AKI despite its widespread use in patients with acute and chronic kidney disease. Because we are excluding patients who are pre-renal, we are minimizing the risk of volume depletion.

Sample Size:

The study team aims to enroll 200 patients with AKI.

First and foremost we are looking to determine if we can replicate the success of our pilot data in a larger multi-center investigation. In powering the overall validation study we assumed 80% power and 5% alpha with this analysis being performed using SAS, Cary, NC, USA. [14] We used a conservative approximation to the variance that assumes independence of the binary variables to calculate power. To investigate the utility of the FST to predict the progression from Stage 1 AKI to Stage 3 we have provided a **Table 6** which demonstrates the change in the True Positive Rate (ΔTPR) based on the event rate and the risk threshold for defining high risk. Recall that the TPR is equivalent to the number of True Positives divided by the True Positives plus the False Negatives ($\text{TPR} = (\text{TP})/(\text{TP}+\text{FN})$) and that this is the equivalent of McNemar's test. [15] Moreover it is important to note that ΔTPR is the equivalent of the Net Reclassification

Index (NRI) for those with the event (Progression to Stage 3 AKI). Practically, this same Table

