demonstrates the minimum detectable change in the False Positive Rate (ΔFPR). The FPR is the number of False Positives divided by the false positives plus the True Negatives ($\text{FPR} = ((\text{FP})/(\text{FP}+\text{TN}))$). Additionally, the $\text{FPR} = 1 - \text{Specificity}$ and perhaps more importantly, ΔFPR is

Table 2 - Detectable change in the Percentage of cases classified as high risk by adding biomarkers to the clinical model.					
Total Sample Size	Event Rate	Expected Number of AKI Progressors (Cases)	10% Classified as High Risk without biomarker	20% Classified as High Risk without Biomarker	50% Classified as High risk Without biomarker
150	15%	22.5	0.21	0.30	0.36
150	30%	45	0.16	0.20	0.26
150	45%	67.5	0.13	0.17	0.22
200	15%	30	0.20	0.28	0.34
200	30%	60	0.15	0.19	0.25
200	45%	90	0.12	0.16	0.20
250	15%	37.5	0.19	0.26	0.32
250	30%	75	0.14	0.18	0.23
250	45%	112.5	0.11	0.15	0.19
300	15%	45	0.18	0.24	0.30
300	30%	90	0.13	0.17	0.21
300	45%	135	0.10	0.14	0.17

equivalent to the NRI
Non Event (non-
progression to Stage 3).
Thus one could look at
Table 6 and view these
numbers as the NRI for
Non-Events.

For the
purpose of this
analysis we have
varied the cohort
sample size as well as
the event rate
(progression). Event
rate variation accounts
for the limited data on
progressive AKI in the

existing literature. While our pilot data (n=77) demonstrated an event rate 32% [11], previously published studies have had varied rates from TRIBE AKI's (13%) [16], EARLY-ARF's (33%) [17] and Siew's et al (29%) [18]. As such a rate progression rate of 30% seems appropriate. To interpret Table 2 if we assume we have 200 individuals with a 30% AKI progression rate (60 cases /AKI progressors) we will be able to detect improvements of 0.15-0.25 in the % of cases classified as high risk (Δ TPR=NRI events). Inversely, for the same cohort and event rate we would be able to detect identical improvements in the Δ FPR (= NRI for non-events). **Thus with 200 subjects and a 30% event rate we would be able to detect small to medium sized improvements in reclassification (NRI events + NRI non-events =Total NRI 0.30-0.50)[19]**

Endpoints and Definitions

AKI – an increase in serum creatinine of >0.3 mg/dL or 50% increase from baseline over 48 hours or an increase to greater than or equal to 150 to 200 percent from baseline or sustained oliguria (mean output of <0.5 cc/kg/hr for 6 hours).

Non-renal recovery

- (1) Patients who require RRT within 14d of enrollment

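### The powered reclassification gains are labelled small to medium, but on the plan's one-threshold scale they are large, and 0.30 to 0.50 is not the detectable total NRI

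*Combined protocol and SAP*

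**What the plan says.** All of this is in the combined protocol and SAP, section D.

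- **Size and error rates.** Under Sample Size: "The study team aims to enroll 200 patients with AKI", and "In powering the overall validation study we assumed 80% power and 5% alpha". Sidedness is not stated.
- **Quantity powered.** The change in true positive rate (TPR) at a threshold defining high risk. The section says "this is the equivalent of McNemar's test" and equates this change with the NRI among events. It equates the change in false positive rate (FPR) with the NRI among non-events.
- **Variance.** "We used a conservative approximation to the variance that assumes independence of the binary variables to calculate power".
- **Event rate.** "As such a rate progression rate of 30% seems appropriate", which gives 60 progressors among 200.
- **Detectable change.** Table 2 (called Table 6 in parts of the text) has columns for the share called high risk beforehand, starting with "10% Classified as High Risk without biomarker", then 20% and 50%. For 200 patients and 30% events the entries are 0.15, 0.19 and 0.25.
- **Conclusion.** The same changes are claimed for the FPR. The two are added to a total NRI of 0.30 to 0.50, and the text says "we would be able to detect small to medium sized improvements in reclassification". The label has a citation but no numerical benchmark.

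The Statistical Analysis section makes this NRI the primary analysis. It names neither the risk threshold nor the clinical model to be improved upon.

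**The concern.** With a single high-risk threshold, the total NRI is the rise in sensitivity plus the rise in specificity. On that scale the stated gains mean sensitivity going from 10% to 25%, 20% to 39%, or 50% to 75%, with an equal improvement among non-events. Few readers would call that small to medium.

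Two further features suggest that the total was not derived as a total. The 140 non-events are given the same detectable change as the 60 events. And at a 10% baseline, a fall of 0.15 in the FPR cannot occur.

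This sentence is the stated justification for 200 patients in the primary analysis. The plan also measures NGAL, TIMP-2, IGFBP7 and possibly other markers. A reader who trusts the sentence could take a non-significant NRI for one of them as evidence that it adds nothing, when such a result would be expected for a marker of modest value.

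**Working it through.** **1. Reproducing the plan's figures.** Inputs from the Sample Size section: 60 cases, 80% power, 5% alpha (two-sided assumed), baseline share p = 0.10, 0.20 or 0.50. The closest formula found uses the baseline variance only:

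detectable change = (1.960 + 0.842) × √(2p(1 − p)/60)

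| p | Computed | Table 2 | Power at the Table 2 value |
|---|---|---|---|
| 0.10 | 0.153 | 0.15 | 78% |
| 0.20 | 0.205 | 0.19 | 74% |
| 0.50 | 0.256 | 0.25 | 78% |

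The two quoted ends reproduce to within 2 points of power; the middle entry does not. The formula matches all 18 cells for 250 and 300 patients and none for 150. A two-sided McNemar test under independence with 60 cases gives 0.209, 0.242 and 0.251, so it matches only the 50% column.

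**2. The detectable total.** Take the plan's figures at face value. The implied standard error (SE) of the TPR change is 0.15/2.802 = 0.0535 at the low end and 0.25/2.802 = 0.0892 at the high end. For 140 non-events at the same baseline share, multiply by √(60/140) = 0.655, giving 0.0351 and 0.0584. Events and non-events are different patients, so the variances add:

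- Low end: 2.802 × √(0.0535² + 0.0351²) = 0.18
- High end: 2.802 × √(0.0892² + 0.0584²) = 0.30

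If the FPR SE is set equal to the TPR one, as the plan implies, the results are 0.15 × √2 = 0.21 and 0.25 × √2 = 0.35. Either way, simple addition (0.30 to 0.50) overstates the total NRI at which power reaches 80%. These ranges inherit the plan's SEs. The low end is the softer one, because the McNemar calculation in step 1 does not reproduce 0.15.

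**3. What a modest marker would add.** Assumptions, not in the documents: binormal scores, a marker independent of the clinical score within events and non-events, a cut at 30% risk (the event rate), clinical-model AUC 0.65 to 0.80, and d = 0.5 standing for a medium marker. With m = √2 × Φ⁻¹(clinical AUC) and D = √(m² + d²),

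NRI = 2[Φ(D/2) − Φ(m/2)].

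For AUC 0.70: m = 0.742, D = 0.895, NRI = 2(0.6727 − 0.6447) = 0.056. Power is from a two-sided 5% Wald test with 60 events and 140 non-events, each group's variance being (discordant share − change²)/n.

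| Clinical AUC | NRI, d = 0.5 | Power, large-sample | Power, simulated |
|---|---|---|---|
| 0.65 | 0.07 | 17% | 18% |
| 0.70 | 0.06 | 14% | 15% |
| 0.75 | 0.04 | 12% | 12% |
| 0.80 | 0.03 | 10% | 11% |

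With thresholds also set so that baseline sensitivity is 10%, 20% or 50%, as in Table 2, the NRI reaches 0.09 and power ranges over 10% to 37%. Under the plan's independence variance the range is 6% to 24%.

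**4. The furosemide test itself.** Preliminary Studies gives a stand-alone AUC of 0.87 for urine output at two to five hours, so d = √2 × Φ⁻¹(0.87) = 1.59. Under the assumptions of step 3, for clinical AUC 0.65, 0.70, 0.75 and 0.80:

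- the NRI is 0.39, 0.33, 0.28 and 0.23;
- power is 99%, 98%, 95% and 90%;
- power under the independence variance is 98%, 93%, 85% and 74%.

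**The case against.** **The label may suit another NRI.** For a category-free NRI, d = 0.5 gives 0.395 with about 74% power, and 0.30 to 0.50 corresponds to d of about 0.38 to 0.64. On that scale the label would be fair. But the section equates the NRI components with changes in TPR and FPR at a threshold and invokes McNemar's test. Those identities hold only for the one-threshold form, and the Statistical Analysis section refers back to that discussion. The category-free reading may explain the label; it does not rescue it.

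**The main purpose is adequately powered.** This stands. The stated first aim is to replicate the pilot furosemide result, and step 4 shows good power for a marker that strong. A reader might infer that the study is too small for its main question, or that 0.30 to 0.50 exceeds anything the pilot supports. The documents support neither inference. Added to a clinical AUC of 0.70, the pilot AUC gives an NRI of about 0.33. The pilot's 200 ml cut-off had sensitivity 87.1% and specificity 84.1%, a sum of 0.712 above chance. That is 0.42 more than the 0.289 of a clinical model with AUC 0.70.

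**The power figures for modest markers rest on outside assumptions.** Also true. The documents define no medium effect and give no clinical-model AUC, so only a range is defensible, and calling the effect very large would be equally without a benchmark.

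**The harm is conditional.** No text plans to declare a marker useless after a non-significant NRI, and ROC analyses accompany the NRI. The risk lies in how the sentence would be read.

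**Conclusion.** The point holds in limited form. On the plan's own scale, the small-to-medium label is unsupported, and the component gains it describes are large. The 0.30 to 0.50 is not the detectable total: taking the plan's implied standard errors, a joint test reaches 80% power at about 0.18 to 0.30 (0.21 to 0.35 with equal standard errors). In that respect the plan understates its sensitivity to total NRI while overstating what kind of marker it can detect.

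For an assumed d = 0.5 marker, power is about 11% to 18% with a cut at 30% risk and clinical AUC 0.65 to 0.80, and 6% to 37% across the thresholds and variance assumptions tried. Every value is far below 80%. This is a shortfall for added biomarkers of modest value. It is not evidence that 200 patients are too few for the furosemide question, where power is about 90% or more if the pilot strength holds and the model's own discordance is used.

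**What to change.** In the Sample Size section:

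1. Remove the small-to-medium label.
2. State that the NRI is two-category, and name the risk threshold and the clinical model.
3. Replace 0.30 to 0.50 with the detectable total NRI from a joint test with 60 events and 140 non-events, showing the formula and the sidedness. Do not claim an FPR fall larger than the baseline FPR.
4. Say that markers of modest added value are not reliably detectable at this size.

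In the Statistical Analysis section, commit to reporting each NRI with its 95% interval, and state that a non-significant NRI alone will not be read as showing no added value.

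The cost is a recalculation and some rewording, with no change to the sample size or study conduct. The numerical total becomes smaller, but the described capability reads less favourably for modest markers.

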The Effect of Loop Diuretics on Severity and Outcome of Acute Kidney Injury

RESEARCH PLAN

A. Specific Aims

The goal of the study is to determine the severity of acute kidney injury (AKI) early in the clinical course of the disease. Patients who suffer from acute kidney injury can have one of four potential outcomes (1) recovery of kidney function without need for dialysis (2) recovery of kidney function with need for dialysis (3) need for dialysis without renal recovery, and (4) death. The goal of the study is to determine if we can identify which clinical course will occur early in the course of the disease. 5) We seek to determine how well physicians caring for those with AKI can predict the clinical course compared to novel biomarkers of AKI. 6) we seek to determine the association between this clinical course and 3 year patient outcomes.

B. Background and Significance

AKI is a very common disease in patient admitted to the hospital. However, despite advances in supportive care, patients with AKI carry a high mortality rate (50% to 70%).[1] AKI affects nearly 5 percent of all hospitalized persons and as many as 15 percent of critically ill patients. [1, 2] Currently, there are no FDA approved therapeutic agents for the treatment or prevention of AKI.

Recently, at a large international consensus meeting held in Vancouver, BC,[3] the single most important question that was raised by this was the question of when to initiate renal replacement therapy (e.g dialysis). Retrospective studies suggest that the early initiation of renal replacement therapy (RRT) improves outcome. [4-7]

However, a significant subset of patients with AKI recovers without the need for RRT. Many clinicians tend to take a “wait and see” approach because they do not want to dialyze a patient who is destined to recover renal function without the need for RRT. Therefore, it is vitally important to know early in the course which patients with AKI are likely to progress to RRT.

C. Preliminary Studies

The majority of studies on the timing of initiation of dialysis have been case series with historical controls or retrospective case-control series that were performed early after the routine clinical use of dialysis was first introduced. For this reason, the BUN at the initiation of dialysis in the "early" treatment group in these previous studies were high by today's standards.

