- (2) Patients who die before 14d, and whose serum creatinine remains >2.0 mg/dl over baseline creatinine at the time of death
- (3) Patients who die before 14d and whose urine output is less than 400cc/24 hours at the time of death

Renal Recovery

- (1) Patients who do not require RRT and survive 14d or are discharged prior to 14 days
- (2) Patients who die before 14d with a serum creatinine >2.0 mg/dl above their baseline AND with a urine output >400cc/24 hours

Statistical Analysis

Patients will be followed for 30 days or until hospital discharge, whichever occurs first. Need for dialysis, serum creatinine, urine output, medication regimens, and mortality will be assessed. Primary analysis will be based on the net reclassification index as discussed in the sample size section above, additionally we will look at the more traditional receiver operating characteristics (ROC) of urine output and urinary sediment score and biomarkers after furosemide challenge to predict AKI progression. Additionally, time to AKI progression and renal recovery/non-recovery will be assessed. Patient outcomes will be stratified by entry criteria and baseline renal function. We will be looking at the long term, (3 year) outcomes in this cohort as well. However given the focus of this study is to identify severe AKI early in the clinical course and that rates of morbidity and mortality in our ICU- AKI cohort are extremely high, we are not sufficiently powered to look at long term outcomes and this aspect of the study is somewhat exploratory and will serve as pilot data for future studies.

Study Procedures

1. Identify appropriate patients via inclusion/exclusion
2. Consent patient or legal representative
3. Draw 7cc of blood, collect 50cc of fresh urine
4. Bolus dose of furosemide
5. Assess urine output response over the next 6 hours
6. Match urine output with intravenous isotonic saline, 1 ml for 1 ml for 6 hours (at the discretion of the clinically treating team – if they feel diuresis is needed clinically they can decide to hold the intravenous fluids – this has not changed from prior submission)
7. Draw 7cc of blood, collect 50cc of fresh urine 2 hours after the furosemide
8. Draw 7 cc of blood; and another 50cc of urine the following morning at 24 hours post dose
9. Draw 7 cc of blood; and another 50cc of urine at the time of ICU discharge
10. Draw 7 cc of blood; and another 50cc of urine at the time of hospital discharge

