11. Patient to receive phone call 30 days following the administration of Furosemide – with ascertainment of any recent laboratory samples outside of the University of Chicago
12. Patient to receive phone call 60 days following the administration of Furosemide - with ascertainment of any recent laboratory samples outside of the University of Chicago
13. Patient to receive phone call 90 days following the administration of Furosemide - with ascertainment of any recent laboratory samples outside of the University of Chicago
14. Telephone contact yearly following furosemide administration for 3 years

E. Study Population

The study population will be all patients who develop AKI in the hospital. A wide range of ages over 18 years old and different ethnic background will be included.

Inclusion criteria

- Age: 18 years and older

- Gender: Both
- Increase in serum creatinine of 0.3 mg/dl within 48 hrs or an increase of greater than or equal to 150 to 200 percent from baseline or sustained oliguria (mean output of <0.5 cc/kg/hr for 6 hours).
- Written informed consent
- Patients who already have a indwelling bladder catheter

Exclusion criteria

- Patients under 18-year-old
- Voluntary refusal or missing written consent of the patient or the designated legal representative
- Patients with advanced Chronic Kidney Disease – as defined by a baseline GFR of < 30 ml/min as calculated by the MDRD equation
- Patients with renal transplantation
- Patients with an allergy or sensitivity to loop diuretics
- Patients with a serum K < 3.0 meq/L
- Patients with a serum Mg < 1.0 meq/L
- Patients with a history of hearing loss
- Patients receiving aminoglycosides
- Pregnancy
- Patients with nephrostomy tubes or any type of urinary diversion
- Patients with a clinical syndrome consistent of pre-renal AKI
 - o Defined by fractional excretion of Na of <1% and no evidence of the urinary casts, or
 - o Patients that are under-resuscitated as deemed by treating clinical team, or
 - o Patients who are actively bleeding
- Patients with a clinical syndrome of post-renal AKI
 - o Any radiological study that shows hydro-ureter, or
 - o Clinical scenario wherein urinary obstruction is considered a likely possibility for the cause of AKI

Gender and Minority Inclusions

AKI affects men and women approximately equally, and there is no known racial susceptibility to AKI. Thus, the study is expected to include both male and female subjects, and a significant number of minority subjects.

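### The two-class recovery endpoint merges recovery after dialysis with dialysis without recovery and gives death no class, so it does not match the four courses in the aims

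*Combined protocol and SAP*

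**What the plan says.** Section A (Specific Aims) lists four outcomes. The first is recovery without dialysis, and the list goes on: "2) recovery of kidney function with need for dialysis (3) need for dialysis without renal recovery, and (4) death". The stated purpose is to tell at an early stage which of these a patient will follow. Item 5 of that section compares physicians with biomarkers in predicting the course, and item 6 relates the course to 3-year outcomes.

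Section D, Endpoints and Definitions, gives two classes.

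- Non-renal recovery has three rules. The first reads "Patients who require RRT within 14d of enrollment". The second takes in deaths before day 14 with creatinine still more than 2.0 mg/dl above baseline. The third takes in deaths before day 14 with a daily urine output under 400 cc.
- Renal Recovery has two rules. The first reads "Patients who do not require RRT and survive 14d or are discharged prior to 14 days". The second takes in deaths before day 14 in which creatinine is more than 2.0 mg/dl above baseline but daily urine output exceeds 400 cc.

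Section D, Statistical Analysis, bases the primary analysis on the net reclassification index (NRI) described under Sample Size, which concerns progression to Stage 3. ROC analyses of AKI progression are added. Recovery versus non-recovery is a further, additional analysis. In-hospital follow-up runs to day 30 or discharge, whichever is first, and records dialysis, creatinine, urine output and death. Calls follow at days 30, 60 and 90 and then yearly for 3 years. Item 13 of Study Procedures reads: "Patient to receive phone call 90 days following the administration of Furosemide".

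**The concern.** Section A treats dialysis and recovery as two separate facts about a patient, and crosses them. The endpoint section makes the first settle the second: a patient dialysed by day 14 is non-recovered, whatever happens next. The distinction that the aims draw between courses 2 and 3 is then lost in the only outcome variable that the plan defines.

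At stake are the recovery/non-recovery analysis and Aim 6, which needs a variable for clinical course and has none. If the four courses are left to be defined at analysis, both the cut-offs and the time point could be chosen after the data have been seen.

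**Working it through.** The plan gives no figure to reproduce here, so the check is to apply the five written rules literally to hypothetical patients from each course. Cr high means creatinine more than 2.0 mg/dl over baseline; UO is urine output in cc per 24 hours.

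| Hypothetical patient | Section A course | Rules met |
|---|---|---|
| No RRT, alive | 1 | Recovery (1) |
| RRT day 3, off by day 10, alive | 2 | Non-recovery (1) |
| RRT day 3, still on RRT, alive | 3 | Non-recovery (1) |
| No RRT, dies day 8, Cr high, UO 200 | 4 | Non-recovery (2) and (3) |
| No RRT, dies day 8, Cr high, UO 800 | 4 | Non-recovery (2) and Recovery (2) |
| No RRT, dies day 8, Cr not high, UO 800 | 4 | None |
| RRT day 3, dies day 8, Cr high, UO 800 | 4 | Non-recovery (1) and (2), and Recovery (2) |
| No RRT, dies day 20 | 4 | Recovery (1) |
| First RRT day 18, alive | 2 or 3 | None, or Recovery (1) |

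Four results follow.

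1. Rows 2 and 3 carry the same code. Non-recovery (1) sets no condition on later status. Recovery (1) asks for no RRT, and Recovery (2) applies only to deaths. So no survivor dialysed by day 14 is coded simply as recovered.
2. Death is spread over both classes, and in one row falls in neither. A death on day 20 without RRT counts as renal recovery.
3. The rules for early deaths overlap: with high creatinine and output above 400, both classes apply. They also leave a gap, when creatinine is not high and output is above 400.
4. First RRT on day 18 meets no rule if the no-RRT condition in Recovery (1) has no time limit. It is coded as recovery if that condition means by day 14.

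The first result was tested against another way of parsing Recovery (1), in which discharge before day 14 is enough on its own. A patient dialysed on day 3 and discharged on day 12 would then meet Recovery (1) and Non-recovery (1) together, and so would a patient discharged still on dialysis. Courses 2 and 3 remain unseparated.

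No other section defines recovery after dialysis, a four-category outcome, or an analysis of one.

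**The case against.** The best defence is that the split on RRT is the study's hypothesis. Section D defines severe AKI as AKI that will need RRT, and Section B says that clinicians need to know who will progress to it. Early RRT is therefore a coherent adverse outcome. That stands, and it is a reason to keep the endpoint. It does not justify the label of non-recovery when Section A allows recovery after dialysis.

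A reader might also infer more than the documents support:

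- *That the first aim cannot be answered.* Dialysis, creatinine and death are recorded in hospital. Dialysis and death are followed at the later calls, with consent to registry linkage. The four courses could be derived; what is missing is a definition, a time point and an analysis.
- *That the main result is compromised.* The primary NRI and the ROC analyses concern AKI progression and do not use these classes.
- *That predictors are tested only against RRT.* They are tested against AKI progression, and the physician survey also covers death, readmission and return home.
- *That the code is permanent.* The text gives no rule for reclassification, but it does not say that the code is fixed.
- *That the 3-year association will be diluted.* Nothing says that the long-term analysis uses the 14-day classes, and Statistical Analysis calls that work exploratory and underpowered.

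**Conclusion.** The mismatch is real and follows from the wording alone. The two classes merge courses 2 and 3 for survivors dialysed by day 14, give course 4 no class, and handle some deaths twice or not at all. The secondary recovery analysis as written cannot separate the four courses, and Aim 6 lacks a definition of clinical course.

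The size cannot be stated. The documents give neither the expected number of patients needing RRT nor the share who later come off it. Rates could be assumed: 10 to 20% of 200 patients (20 to 40) needing RRT, and 30 to 60% of those later coming off it, would put 6 to 24 patients in course 2 (20 × 0.30 to 40 × 0.60). Neither rate is in the documents, and the finding does not rest on them.

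This is a defect in a secondary endpoint and in its match to the stated goal. It should be settled before analysis.

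**What to change.** Keep RRT within 14 days as a separate need-for-RRT endpoint and stop labelling it non-recovery. Prespecify a four-category outcome at day 90:

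1. alive, no RRT at any time to day 90, with kidney recovery judged by a stated creatinine criterion;
2. alive, any RRT to day 90, and dialysis-free at day 90 under a stated definition;
3. alive and on dialysis at day 90;
4. dead by day 90.

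State how survivors without RRT who miss the creatinine criterion are handled, and which creatinine value counts, since after discharge only outside laboratory results are available. Count first RRT after day 14 or after discharge. Use these classes for the recovery analysis and Aim 6. Putting all deaths to day 90 in class 4 also removes the overlap and the gap in the early-death rules.

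The cost is mainly wording, because RRT use, dialysis status and death are already collected. Status becomes final at day 90 rather than day 14, and some patients will be lost to the call; consented outside records and registry linkage offset this in part. The change does not supply a physician forecast of recovery after RRT, because no survey question asks for one.

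### Renal Recovery (1) lets early discharge stand in for day-14 status and sets no kidney-function condition for survivors, so some unresolved AKI, early deaths and possibly later RRT are labelled recovery

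*Combined protocol and SAP*

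**What the plan says.** All of this is in section D unless noted.

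- **Renal Recovery (1):** "Patients who do not require RRT and survive 14d or are discharged prior to 14 days".
- **Renal Recovery (2):** "Patients who die before 14d with a serum creatinine >2.0 mg/dl above their baseline AND with a urine output >400cc/24 hours".
- **Non-renal recovery (1):** "Patients who require RRT within 14d of enrollment". It is not limited to RRT given in hospital.
- **Non-renal recovery (2) and (3):** "Patients who die before 14d, and whose serum creatinine remains >2.0 mg/dl over baseline creatinine at the time of death", and "Patients who die before 14d and whose urine output is less than 400cc/24 hours at the time of death".
- **Statistical Analysis:** "Patients will be followed for 30 days or until hospital discharge, whichever occurs first". Over that period, "Need for dialysis, serum creatinine, urine output, medication regimens, and mortality will be assessed". Recovery/non-recovery is listed as an additional analysis. The primary analysis is the net reclassification index, sized on progression to Stage 3.
- **Study Procedures, step 11:** "Patient to receive phone call 30 days following the administration of Furosemide", with outside laboratory results sought.
- **Long Term Follow-up:** monthly contact for three months, covering dialysis and mortality among other outcomes, and consent for linkage to SSDI and USRDS.

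**The concern.** Two features of Recovery (1) can give a label that disagrees with the patient's actual course.

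First, it contains no creatinine or urine-output condition. Those conditions apply only to patients who die before day 14. Yet section A speaks of recovery of kidney function, and the opening of section D describes less severe AKI as AKI that improves without RRT. Under the rule, improvement is not required of a survivor.

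Second, leaving hospital before day 14 satisfies the rule with no check of what happened between discharge and day 14. Follow-up in the Statistical Analysis section stops at discharge.

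Both features tend to move failures into the recovery class, and the second depends on discharge timing, which is not a measure of kidney function. At stake are the non-recovery count, the time-to-recovery analysis, and the apparent accuracy of the furosemide response against this endpoint.

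**Working it through.** No figure in the plan derives from this definition, so there is none to reproduce. The check applies the rules to each type of patient under both possible groupings of Recovery (1):

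- **A:** no RRT, and (alive at day 14 or discharged early).
- **B:** (no RRT and alive at day 14), or discharged early.

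| Patient | Recovery (1), A | Recovery (1), B | Non-recovery rule met |
|---|---|---|---|
| 1. In hospital and alive at day 14, no RRT, creatinine >2.0 mg/dl above baseline | Yes | Yes | None |
| 2. Discharged early, alive and without RRT to day 14, creatinine >2.0 mg/dl above baseline | Yes | Yes | None |
| 3. Discharged early without RRT, dies before day 14 | Yes | Yes | (2) or (3), only if creatinine or urine output at death is known and meets the criterion |
| 4. No RRT in hospital, discharged early, RRT started by day 14 | No if all RRT to day 14 counts; yes if only in-hospital RRT counts | Yes | (1) |
| 5. RRT in hospital, then discharged before day 14 | No | Yes | (1) |
| 6. In hospital and alive at day 14, had RRT | No | No | (1) |

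Rows 1 to 3 do not depend on the grouping. In row 3 the plan describes no procedure for obtaining creatinine or urine output at a death outside hospital, so the recovery label would usually stand. Row 4 depends on ascertainment and precedence. Row 5 is a problem only under B, where the patient falls in both classes. Row 6 is handled correctly.

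**The 2.0 mg/dl value.** A patient who dies before day 14 with creatinine more than 2.0 mg/dl above baseline and urine output above 400 cc/24 h meets Non-recovery (2) and Recovery (2) together. A patient without RRT who dies in hospital before day 14 with creatinine no more than 2.0 mg/dl above baseline and urine output above 400 cc/24 h meets no rule at all. The threshold therefore needs reconciling before it is reused.

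**Size, on assumptions only.** The documents give neither the share discharged before day 14 nor the later event rates.

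- *Row 4:* patients affected = 200 × share discharged early × share of those starting RRT by day 14. With 20% and 2%: 200 × 0.20 × 0.02 = 0.8. With 60% and 10%: 200 × 0.60 × 0.10 = 12.
- *Effect on apparent specificity:* suppose 60 of 200 are true failures (borrowing the plan's 30% Stage 3 rate) and a fraction m of them is scored as recovered regardless of the test result. Take the pilot sensitivity of 87.1% and specificity of 84.1%, which were for Stage 3 progression. Apparent specificity = (140 × 0.841 + 60m × 0.129) / (140 + 60m).
  - m = 0.10 (6 patients): (117.74 + 0.774) / 146 = 81.2%.
  - m = 0.30 (18 patients): (117.74 + 2.322) / 158 = 76.0%.
  - Sensitivity is unchanged in this set-up.

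These figures show direction and possible scale. They are not estimates for this trial.

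**The case against.** The strongest defence is that the rules mostly work when read sensibly. Recovery (1) opens with the absence of RRT, so under grouping A a patient dialysed in hospital and then discharged is non-recovery only. Non-recovery (1) already covers RRT after discharge up to day 14. The 30-day contact and the linkage exist, and nothing says they will be ignored. This stands. A reader might infer that every early discharge is scored as recovered, or that RRT status is disregarded. The first is true only under grouping B. The second is not supported: the RRT problem is one of ascertainment and precedence.

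A reader might also count every post-discharge death as a failure wrongly scored as recovered. The plan does not treat death alone as non-recovery, because Non-recovery (2) and (3) add a kidney criterion. What can be said is that such a death meets the recovery rule without that criterion being examined.

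Nor is it an error in itself that a Stage 3 progressor is later labelled recovered. Peak severity and later recovery are different things, and section A lists recovery even after dialysis. The difficulty is a label of recovery where no improvement was required.

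Finally, this is an additional analysis. That stands and limits the weight of the point, but it does not remove rows 1 to 3.

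**Conclusion.** The point holds in this form. On any reading, Recovery (1) labels as recovered a survivor without RRT at any creatinine, and its terms are met by an early discharge without RRT who dies before day 14. Post-discharge RRT by day 14 is non-recovery under the plan's own rule, but is at risk of being scored as recovery because neither the data source nor the precedence is stated.

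The size cannot be determined from the documents. The illustrative 0.8 to 12 patients for post-discharge RRT rests wholly on assumed rates. There is no basis for sizing the number of survivors with unresolved creatinine. A reader might infer that the main result is compromised, but the primary net reclassification index and the sample size rest on Stage 3 progression and do not use this definition. The change should be made before the recovery/non-recovery analysis is run.

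**What to change.** 1. Delete the early-discharge alternative from Recovery (1). For patients discharged before day 14, assign day-14 RRT and vital status from the 30-day contact (asking the date of any RRT), outside records and the SSDI/USRDS linkage.
2. State that Non-recovery (1) takes precedence over any recovery rule. Report as undetermined the early discharges who cannot be reached or linked, and those who die after discharge with unknown creatinine and urine output. Add a sensitivity analysis that scores the undetermined patients each way.
3. Either rename the survivor class as alive and RRT-free at day 14, so that the label claims no more than the rule tests, or add a sensitivity analysis comparing the last available creatinine (day 14 or discharge) with the plan's value of 2.0 mg/dl above baseline. Before doing the latter, reconcile the use of that value in both Non-recovery (2) and Recovery (2), and assign a class to deaths that meet neither.

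The contacts, linkage consent and in-hospital creatinine are already planned, so no new visit or sample is needed. The cost is that some patients become undetermined and one or two analyses are added.
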